5.2 Baseline

Unless otherwise specified, baseline value will be defined as the last non-missing assessment prior to or concurrently with the first study treatment dosing (including unscheduled/retest assessments). If the last non-missing assessment is performed on the same date as the first study treatment administration and time is not available, it is assumed that the assessment took place prior to IP application, per study site training, and the assessment will be considered as baseline, except for adverse events (AEs) and medications starting on the first study treatment dose administration date which will be considered postbaseline.

Average weekly baseline WI-NRS is defined as the average of all non-missing scores reported during the last 7 days prior to treatment if at least 4 of 7 evaluable daily WI-NRS questionnaires

	STATISTICAL ANALYSIS PLAN, Version 1.0
Protocol Number: ARQ-151-312	Sponsor: Arcutis Biotherapeutics, Inc.

available. Daily baseline WI-NRS is defined as the last non-missing assessment prior to or concurrently with the first study treatment dosing. Day 1 WI-NRS score will be used to calculate the value for week 1 only when it is collected after the application of the first study drug. If Day 1 WI-NRS score is collected prior to or concurrently with the application of the first study drug, then the Day 1 WI-NRS score will be included in baseline calculation.

For investigator/subject tolerability assessments, baseline is derived as the measurement taken on the day of first application of study drug.

5.3 Reference Start Date and Analysis Day

Analysis day will be calculated from the first study treatment administration date and will be used to derive start/end day of assessments or events.

Analysis day = (Date of event – Date of first dose administration) + 1 if date of event is on or after the date of first dose administration of study treatment;

= (Date of event – Date of first dose administration) if date of event is before the date of first dose administration of study treatment.

In the situation where the assessment/event date is partial or missing, analysis day will be missing.

5.4 Windowing Conventions

Visits will be analysed as scheduled. Unscheduled, early termination visits, and/or retest measurements will only be included if a scheduled measurement is not available and the early termination or unscheduled/retest measurement falls within the analysis visit windows as described in Table 2, Table 3, and Table 4 when appropriate. Unscheduled/retest measurements will be listed.

If there is more than one assessment for a given timepoint and analysis visit when a scheduled measurement is not available, the assessment closest to the target day will be considered.

Table 2 Analysis Visit Windows for Efficacy Endpoints, Vital Signs, CDI-2, PHQ-8, PHQ-A, C-SSRS and Local Tolerability Assessment

Analysis Visit	Target Day	Lower Limit	Upper Limit
Week 1	8	2	11
Week 2	15	12	22
Week 4	29	23	43

	STATISTICAL ANALYSIS PLAN, Version 1.0
Protocol Number: ARQ-151-312	Sponsor: Arcutis Biotherapeutics, Inc.

Table 3 Analysis Visit Windows for Clinical Laboratory, Physical Examination and PK assessment

Analysis Visit	Target Day	Lower Limit	Upper Limit
Week 4	29	23	43

Table 4 Windows for the derivation of Average Weekly WI-NRS

Days for calculation of weekly average	Week (Derived)
(-7, -1)*	Baseline
(1, 7)	Week 1
(8, 14)	Week 2
(15, 21)	Week 3
(22, 28)	Week 4

^{*} Day 1 WI-NRS score will be used to calculate the value for week 1 only when it is collected after the application of the first first study drug. If Day 1 WI-NRS score is collected prior to or concurrently with the application of the first study drug, then the Day 1 WI-NRS score will be included in baseline calculation.

Note: With the following caveat, if more than one WI-NRS score is available on the same day, the worst score of the day will be considered in the analyses. The caveat is that if a subject has two WI-NRS assessments on Day 1 and one of them was collected before the first study treatment dosing while the other one was collected after the first study drug dosing. Under such circumstances, the assessment collected before the first study drug dosing will be considered for the Baseline analysis visit while the assessment collected after the first study drug dosing will be considered for the Week 1 analysis visit.

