5.9. Treatment Stopping Rules

If a subject has non-cutaneous adverse events of concern, clinically significant laboratory values or any condition that the investigator determines could possibly be related to the study drug, the Investigator should immediately contact the Medical Monitor to discuss if the subject should be discontinued from treatment with investigational product.

Treatment for any individual subject will be discontinued if the subject experiences:

- A serious adverse event (SAE) or a clinically significant non-serious AE which in the opinion of the Principal Investigator or Medical Monitor warrants discontinuation from the study for that subject's well-being.
- A treatment-emergent severe (Grade 3) laboratory abnormality (confirmed by repeat sample; see Appendix 13 for more information).

A subject with a PHQ-8 or modified PHQ-A score ≥ 15 should receive immediate referral to a mental health professional, and Investigators in consultation with the mental health professional should consider interruption or discontinuation of the study drug.

• Subjects with a PHQ-8 or modified PHQ-A score of 10-14 should be referred to a mental health professional for evaluation, regardless of the reason for their change in score

Subjects with a CDI-2 raw total score of \geq 32 should be referred to a mental health professional, and Investigators in consultation with the mental health professional should consider interruption or discontinuation of the study drug

• Subjects with a CDI-2 raw score of ≥21 for females and ≥22 for males should be referred to a mental health professional for evaluation

A subject that is experiencing suicidal ideation and behavior should be referred immediately to a qualified mental health care provider and consideration given to discontinuation from study drug.

As noted above, study treatment must be discontinued immediately in the event of a female subject's pregnancy.

Treatment should be interrupted:

• If a subject develops an application site reaction with the clinical appearance of an 'irritation reaction', and with a severity of a Dermal Response Score of 5 (erythema, edema and papules) or greater on the scale of Berger and Bowman, treatment should be interrupted for up to one week and may then be resumed if the reaction has, in the opinion of the Investigator, adequately resolved.

Treatment should be discontinued:

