6.6. Safety Analysis

Descriptive statistics will be calculated for quantitative safety data and frequency counts will be compiled for classification of qualitative safety data. The safety population will be used for these analyses.

Adverse Events:

The subject incidence of treatment-emergent adverse events (TEAE) will be summarized overall, by severity, and by attribution.

Clinical Laboratory Results:

Shifts in clinical laboratory parameters from baseline to worst post-baseline grade will be provided.

Vital Signs:

The subject incidence of >5% weight loss or gain on study will be provided, as well as whether weight loss was explained or unexplained.

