5.8 Handling of Retests, Unscheduled Visits, and Early Termination Data

Retests measurements, Unscheduled measurements, and ET visit assessments will be included in analysis and be summarized via analysis visit windowing according to the windowing conventions in section 5.4.

All data from retest, unscheduled measurements and ET visit assessments will be listed.

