13.2 Clinical Laboratory

Descriptive statistics for the observed values in chemistry, hematology, and quantitative urinalysis, change from baseline and percent change from baseline values will be presented by treatment group at each scheduled visit. For qualitative urinalysis data, the number and percentage of the subjects for each level of result by treatment at each scheduled visit will be provided.

Shift tables from baseline to each postbaseline assessments describing shifts to out-of-normal range will be provided for chemistry, hematology, and qualitative urinalysis. Only subjects with a baseline result and a result at the specified visit for the parameter will be considered.

Listings of abnormal laboratory will be provided for each parameter where a subject had at least one abnormal result.

Laboratory data will be presented in SI units.

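### Laboratory tables use only Week 4 values (Days 23 to 43): earlier or displaced results reach listings but no laboratory table, and the protocol's worst-grade shift table is not in the SAP

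*SAP*

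**What the plan says.** **Window.** SAP 5.4 contains "Table 3 Analysis Visit Windows for Clinical Laboratory, Physical Examination and PK assessment". It has one row: Week 4, target Day 29, limits Day 23 and Day 43.

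**Which values count.** SAP 5.4 sets two conditions for values that are not scheduled measurements. First, "Unscheduled, early termination visits, and/or retest measurements will only be included if a scheduled measurement is not available". Second, the value must be one that "falls within the analysis visit windows as described in Table 2, Table 3, and Table 4 when appropriate". If several candidates remain and there is no scheduled value, "the assessment closest to the target day will be considered". SAP 5.8 sends retest, unscheduled and early-termination data through the same rule: they "will be included in analysis and be summarized via analysis visit windowing according to the windowing conventions in section 5.4". It also says that all such data are listed.

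**Laboratory outputs.** SAP 13.2 plans descriptive statistics by scheduled visit, shift tables to out-of-range values, and a listing of abnormal results. For the shift tables, "Only subjects with a baseline result and a result at the specified visit for the parameter will be considered". No table uses toxicity grade or the worst value.

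**Protocol.** Section 6.6 states: "Shifts in clinical laboratory parameters from baseline to worst post-baseline grade will be provided". Section 6.8 repeats this, and section 6.12 separately plans an out-of-range shift table. Section 5.1.6 allows unscheduled laboratory tests, and section 5.5 asks for the Week 4 procedures at early termination. Among the grounds for stopping treatment, section 5.9 lists: "A treatment-emergent severe (Grade 3) laboratory abnormality (confirmed by repeat sample; see Appendix 13 for more information".

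**The concern.** With one scheduled post-baseline draw, laboratory results at other times arise mainly because something happened: a subject left early, a test was ordered for a suspected problem, or a value was repeated for confirmation. The windowing rule keeps most of these out of the laboratory tables. Laboratory change is a listed safety endpoint (SAP section 2), so the by-arm summary would describe subjects with a value at Day 23 or later, at one time point.

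The worst-grade shift in the protocol is the table that would pick such results up. Without it, no table shows by arm how often laboratory values reached the grade that triggers the protocol's own stopping rule.

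The treatment of laboratory data also differs from the rest of the SAP. Baseline may come from an unscheduled or retest value (SAP 5.2). Table 2, which covers vital signs and the depression questionnaires, runs from Day 2 to Day 43 without a gap (2 to 11, 12 to 22, 23 to 43).

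**Working it through.** The plan gives no figure to reproduce here. The check applies the SAP 5.4 rule to example records.

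**Rule as applied.** (1) If a scheduled Week 4 value exists, use it. (2) If not, take unscheduled, retest or early-termination values on Days 23 to 43 and use the one nearest Day 29. (3) If there is none, the subject has no post-baseline value and is not counted in the shift table.

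| Example record | Value that reaches the laboratory table |
|---|---|
| Unscheduled Grade 3 on Day 12; scheduled normal on Day 29 | Day 29, normal |
| Unscheduled Grade 3 on Day 25; scheduled normal on Day 29 | Day 29, normal |
| Unscheduled Grade 3 on Day 12; early-termination normal on Day 24 | Day 24, normal |
| Early-termination Grade 3 on Day 15 or Day 22; nothing later | None: subject not counted |
| Early-termination Grade 3 on Day 23 | Day 23 value, shown as out of range |
| Unscheduled Grade 3 on Day 24; normal retest on Day 27; no scheduled value | Day 27, normal |

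In the last row the distances to Day 29 are 29 − 24 = 5 and 29 − 27 = 2, so the normal retest is chosen. The second and last rows show that values inside the window can be lost too.

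**Coverage of the treatment period.** Day 2 to Day 29 is 29 − 2 + 1 = 28 days. Day 2 to Day 22 is 22 − 2 + 1 = 21 days. So 21 of 28 days (75%) lie outside any laboratory window.

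**Planned shift tables compared.**

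| Table | Protocol (original) | SAP 13.2 |
|---|---|---|
| Baseline to worst grade after baseline | 6.6 and 6.8 | Absent |
| Baseline to out of normal range | 6.12 | Present, by visit |

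One of two planned tables was carried forward. SAP section 1 says that changes from the protocol are described in section 3.5. That section records even the removal of a categorical tube-weight summary, but nothing about laboratory shifts.

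**Who is exposed to the gap.** Under SAP Table 1, note b, subjects entering under Amendment 2 have laboratory samples after Screening only if aged 12 or older. The gap therefore concerns mainly those subjects, plus younger ones enrolled before that amendment.

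**The case against.** **Listings and adverse event tables exist.** All retest, unscheduled and early-termination data are listed, and abnormal values have their own listing. A laboratory finding with clinical sequelae, or one needing treatment, is an adverse event (Protocol 5.7.1). TEAE tables have no Day 23 limit and include events leading to discontinuation (SAP 13.1). Reasons for leaving the study are tabulated for all randomized subjects (SAP 7.1). A reader might infer that early leavers with abnormal values vanish from the safety report; they do not. What remains is that listings give no rate by arm. Protocol 5.7.1 also generally keeps abnormalities judged not clinically significant out of the adverse event record and, where applicable, has the sequela recorded instead of the laboratory value.

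**A Grade 3 value reported as normal.** A reader might infer this. The documents do not support it: the value is left out of the table, and the Week 4 entry is correct for Week 4. An early leaver without a value in the window is missing, not normal.

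**An undeclared substitution.** A reader might infer that the SAP swapped one table for another without saying so. Section 6.12 shows that the out-of-range table was planned anyway. The SAP follows Amendment 3, whereas the supplied protocol is the original. SAP 3.5 quotes as original a per-protocol definition that the supplied protocol does not contain, so it evidently compares with later text. Amendment 3 may have dropped the worst-grade sentence.

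**A uniform bias toward no effect.** This is not established. If the scheduled Week 4 value is abnormal and its retest normal, the rule keeps the abnormal one. Keeping irregular draws out of a by-visit summary is a defensible convention, and the single time point reflects the visit schedule. Inside the window, an extreme value can also show in the tabulated maximum. These points defend the by-visit table; they do not supply a summary of the worst value.

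**Wider reading of SAP 13.2.** Its shift tables run to each assessment after baseline, which could be read broadly. The next sentence restricts counting to the specified visit, and SAP 5.8 points back to the windows.

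**Conclusion.** On the SAP text alone, the laboratory tables use only Week 4 values. Results from Days 2 to 22, and unscheduled or retest results displaced by a scheduled Week 4 value, appear in listings, and in TEAE tables if they meet the adverse event definition, but in no laboratory summary or shift table.

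The absence of the worst-grade shift from SAP 13.2 is also plain. Whether that is an omission or follows Amendment 3 cannot be settled from these documents.

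The number of subjects affected cannot be estimated: the documents give no rate of early withdrawal, unscheduled testing or Grade 3 values. No efficacy inference is touched. The gap is still worth closing, because tests prompted by a suspected problem are among the values that the rule leaves out of the by-arm summary.

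**What to change.** In SAP 13.2, add a by-arm table of shift from baseline to the worst grade after baseline. Use every result after first application, whether scheduled, unscheduled, retest or early termination, and do not apply the Table 3 window.

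- Name the grading scale. Protocol 6.6 names none, and Appendix 13 is the protocol's only laboratory grading table. If it is used, note its healthy-adult origin for subjects under 18.
- Footnote that unscheduled samples are not drawn evenly across subjects.
- Keep the Week 4 out-of-range shift as the by-visit summary.
- If Amendment 3 removed the worst-grade table, confirm that. If it did not and the table is not restored, declare the removal in SAP 3.5.

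The cost is one additional safety table and a footnote, from data already collected.

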5.5 Derived Variables

All questionnaire scores will be derived by Biostatistics in the ADaM datasets using the formulas defined below, even if calculated scores are present in the EDC database. All pre-calculated scores will be ignored for analysis.

- vIGA-AD Success = vIGA-AD of 'Clear' (0) or 'Almost Clear' (1) plus at least a 2-grade improvement from Baseline.
- Average weekly WI-NRS = Average weekly of the WI-NRS pruritus scores will be
 calculated as the sum of the daily WI-NRS scores reported during a specific week (in a 7day period) of the study divided by the number of days with non-missing scores for that
 week. A minimum of 4 days of observations are needed to calculate average weekly WINRS. Otherwise, the corresponding average weekly WI-NRS will be considered missing.

	STATISTICAL ANALYSIS PLAN, Version 1.0
Protocol Number: ARQ-151-312	Sponsor: Arcutis Biotherapeutics, Inc.

The average weekly WI-NRS results will be presented for analysis visits i.e., Baseline, Week 1, Week 2, Week 3, and Week 4 (see Table 1 Table 4 for the analysis window).

• WI-NRS 4-point reduction = achievement of a 4- point reduction in average weekly WI-NRS pruritus score compared to average weekly WI-NRS baseline, calculated only for the subjects ≥12 years old with average weekly WI-NRS score of ≥ 4 at baseline.

$$\begin{split} \bullet \quad & \text{EASI total score} = 0.1 \; (E_h + I_h + E_{Xh} + L_h) \; A_h + 0.2 \; (E_u + I_u + E_{Xu} + L_u) \; A_u \\ & \quad + 0.3 \; (E_t + I_t + E_{Xt} + L_t) \; A_t + 0.4 \; (E_l + I_l + E_{Xl} + L_l) \; A_l \\ & \quad \text{for subjects $`\geq 8$ years old} \\ & \quad \text{and} \\ & \quad 0.2 \; (E_h + I_h + E_{Xh} + L_h) \; A_h + 0.2 \; (E_u + I_u + E_{Xu} + L_u) \; A_u \\ & \quad + 0.3 \; (E_t + I_t + E_{Xt} + L_t) \; A_t + 0.3 \; (E_l + I_l + E_{Xl} + L_l) \; A_l \\ & \quad \text{for subjects < 8 years old} \end{split}$$

where E, I, Ex, L, and A denote erythema, induration, excoriation, lichenification, and area, respectively, and h, u, t, and l denote head, upper extremities, trunk, and lower extremities, respectively. If a subject turns 8 years old during the study, the formula used at Screening will continue to be used through the study duration of the subject's participation in the study. Scalp, palms, and soles may be treated with investigational product in this study but will be excluded from the EASI assessment.

- EASI-50, EASI-75, EASI-90, EASI-100 = Achievement of at least a 50%, 75%, 90%, or 100% reduction from baseline in the Eczema Area and Severity Index at Week 4
- DLQI Score = sum of the 10 questions (individual questions scored as Very much=3, A lot=2, A little=1, Not at all=0, Not relevant=0, Question 7: Yes=3, if No, then follow the same score as A lot, A little, Not at all), ranging from 0 to 30. If 1 item is missing, it is scored as 0 for that item. If 2 or more items are missing, the score should not be calculated.
- CDLQI Score = sum of the 10 questions (individual questions scored as Very much=3, Quite a lot=2, Only a little=1, Not at all=0; Question 7: if the last week was school time, the question was scored as Very much=3, Quite a lot=2, Only a little=1, Not at all=0, with Prevented school recoded to 3, and if the last week was holiday time, the standard responses apply), ranging from 0 to 30. If 1 item is missing, that item is scored as 0. If 2 or more items are missing, the score should not be calculated.
- DFI Score = sum of the 10 questions (individual questions scored as Very much=3, A lot=2, A little=1; Not at all=0), ranging from 0 to 30. If 1 item is missing, it is scored as 0 for that item. If 2 or more items are missing, the score should not be calculated.

	STATISTICAL ANALYSIS PLAN, Version 1.0
Protocol Number: ARQ-151-312	Sponsor: Arcutis Biotherapeutics, Inc.

- PHQ-8 = sum of the 8 questions (individual questions scored as Not at all=0, Several days=1, More than half the days=2, and Nearly every day=3), ranging from 0 to 24. If more than 1 item is missing the score should not be calculated. If 1 item is missing the score is calculated as (sum of answered items*8)/number of answered items (=7).
- Modified PHQ-A = sum of the 8 questions (individual questions scored as Not at all=0, Several days=1, More than half the days=2, and Nearly every day=3), ranging from 0 to 24. If more than 1 item is missing the score should not be calculated. If 1 item is missing, the score is calculated as (sum of answered items*8)/number of answered items (=7).
- CDI-2 total score is a sum of the 17 questions based on the scoring grid (individual questions scored as much or most of the time=0, often=1, some of the time=2, Not at all=3 for questions Q2, Q7, Q13, Q14, and Q16; individual questions scored as much or most of the time=3, often=2, some of the time=1, Not at all=0 for all other questions), ranging from 0 to 51. All CDI-2 raw scores can be prorated using the following formula, rounding to the nearest whole number:
 - O Prorated score = (Obtained raw score for scale) * (Total # of items on scale/subscale) / Total # items on scale/subscale with responses
 - CDI-2 emotional problem scale is a sum of 9 questions (Q1, Q3-6, Q8, Q10-12). If more than 1 item is missing the score should not be calculated. If 1 item is missing the score is calculated as (sum of answered items*9)/number of answered items (=8).
 - O CDI-2 functional problem scale is a sum of 8 questions (Q2, Q7, Q9, Q13-17). If more than 1 item is missing the score should not be calculated. If 1 item is missing the score is calculated as (sum of answered items*8)/number of answered items (=7).
 - OCDI-2 total score is a sum of 17 questions. If more than 2 items are missing the score should not be calculated. If 1 item is missing the score is calculated as (sum of answered items*17)/number of answered items (=16). If 2 items are missing the score is calculated as (sum of answered items*17)/number of answered items (=15).
- POEM = sum of the 7 questions (individual questions scored as No days = 0, 1 to 2 days = 1, 3 to 4 days = 2, 5 to 6 days = 3, Every day = 4), ranging from 0 to 28. If 1 question is left unanswered this is scored 0 and the scores are summarized and expressed as usual out of a maximum of 28. If 2 or more questions are left unanswered the questionnaire is not scored.

	STATISTICAL ANALYSIS PLAN, Version 1.0
Protocol Number: ARQ-151-312	Sponsor: Arcutis Biotherapeutics, Inc.

• SCORAD = [Overall BSA affected by AD / 5] + [Intensity score*7/2] + subjective symptoms score (pruritus + sleep loss); SCORAD score will be set to missing if information for any of the three measures is missing.

